6.14.2.1. Common Adverse Events

The number and percentages of patients with TEAEs will be summarized by treatment using MedDRA PT for the common TEAEs (occurred in $\geq 1\%$ before rounding in total LY column in the table).

6.14.2.2. Deaths, Other Serious Adverse Events and Other Notable Adverse Events

The number and percentage of patients reported with an SAE during the treatment period will be summarized by treatment using MedDRA PT. A listing of SAEs will be provided.

The number and percentage of patients who permanently discontinued from study treatment due to an AE (including AEs that led to death) during the treatment period will be summarized by treatment using MedDRA PT. Events will be ordered by decreasing frequency in all treatment groups.

6.14.3. Clinical Laboratory Evaluation

As described more fully in compound level safety standards and in the laboratory-related PhUSE white papers (PhUSE 2013; PhUSE 2015), the clinical laboratory evaluations will be summarized as described in [Table KGAC.6.14](#). Hormone analytes are summarized/Plotted similarly for adolescent patients.

Table KGAC.6.14. Analysis for Clinical Laboratory Evaluations

Analysis	Population
Box plots of observed values by visit	mS, mM
Box plots for change values by visit	
Change from baseline to last observations. ANCOVA model with treatment and baseline value in the model.	mS, mM
Scatter plots of baseline-by-maximum values and baseline-by-minimum values	mS, mM
Treatment-emergent abnormal high lab values (ie, patients shifting from a normal/low maximum baseline value to a high maximum postbaseline value) or abnormal low lab values (ie, patients shifting from normal/high minimum baseline value to a low minimum postbaseline value)	mS, mM, mA
Shift tables showing the number of patients who shift from each category of maximum (minimum) baseline observation to each category of maximum (minimum) postbaseline observation. Here categories may be low, normal, or high with cut-offs defined in the compound level safety standards.	mS, mM
Listing of abnormal findings for laboratory analyte measurements, including qualitative measures	All Enrolled

Abbreviations: ANCOVA = analysis of covariance; mA = Modified All Lebrikizumab Safety Population; mM = Modified maintenance Primary Population, mS = Modified Safety Population.

6.14.4. Vital Signs and Other Physical Findings

As described more fully in compound level safety standards and in the laboratory-related PhUSE white papers (PhUSE 2013; PhUSE 2015), vital signs will be summarized similarly to the clinical laboratory evaluation ([Table KGAC 6.15](#)). For vital signs, treatment emergent low and high are based on a combination of a specified value and a change or percentage change for adults and adolescents as defined in the compound level safety standards.

Table KGAC 6.15. Analysis Related to Vital Signs

Analysis	Population
Box plots for observed values by visit	mS, mM
Box plots for change from baseline values by visit	mS, mM
Scatterplots of baseline-by-maximum values and baseline-by-minimum values	mS, mM
Tables with the number and percentage of subjects who shift from normal/high to low (ie, treatment-emergent low) and the number and percentage of subjects who shift from normal/low to high (ie, treatment-emergent high); the limits are defined in the compound level safety standards	mS, mM, mA

Abbreviations: mA = Modified All Lebrikizumab Safety Population; mM = Modified maintenance Primary Population, mS = Modified Safety Population.

6.14.4.1. Adolescent Standardized Growth

Weight, height, and BMI data will be merged to the Centers for Disease Control and Prevention (CDC) standard growth data (released in 2000) by age and gender in order to compare patients' growth with the standard. Z-score and standardized percentile of weight, height, and BMI at each visit will be calculated and compared to the 2000 CDC growth charts. Because of the short duration of controlled period, only All Lebrikizumab Safety Population will be described during Combined Induction and Maintenance Periods.

The z-score and percentile calculations are based on algorithms and data provided by the National Center for Health Statistics. The details are provided in the CDC website (<https://www.cdc.gov/nccdphp/dnpao/growthcharts/resources/sas.htm>) (CDC resources page [WWW]).

The following summaries and plots will be provided:

Table KGAC.6.16. Analysis Related to Adolescent Standardized Growth

Analysis	Population
Summaries for baseline, mean change of actual measure, z-score and standardized percentile of weight, height, and BMI.	mA
Scatter plot of patients' mean weight, height, and BMI standardized percentile versus lebrikizumab exposure time	mA

Abbreviations: BMI = body mass index; mA = All Lebrikizumab Modified Safety Population.

6.14.5. Immunogenicity

An individual sample is potentially examined multiple times in a hierarchical procedure to produce a sample anti-drug antibody (ADA) assay result and may yield a sample neutralizing ADA (NAb) assay result. Treatment-emergent ADA (TE-ADA) are defined as those with a titer 2-fold (1 dilution) greater than the minimum required dilution if no ADAs were detected at baseline (treatment-induced ADA) or those with a 4-fold (2 dilutions) increase in titer compared to baseline if ADAs were detected at baseline (treatment-boosted ADA). A patient is considered TE-ADA positive when at least 1 postbaseline ADA sample meets the definition of TE-ADA.

Compound level safety standards will be followed in the analyses of immunogenicity. Listings of immunogenicity assessments will be provided for the Safety Population. The summary of TE-ADA and NAb status will be produced for the Modified Safety Population during the Induction Period. The summary of the Modified Maintenance Primary Population will be provided for the Combined Induction and Maintenance Periods. For the Modified Maintenance Primary Population, the immunogenicity analysis will be cumulative across both the Induction and Maintenance Periods. Additional assessments of the relationship between immunogenicity and efficacy and TEAE by TE-ADA status will be performed as part of the integrated analysis including other Phase 3 lebrikizumab AD trials.

6.14.6. Special Safety Topics including Adverse Events of Special Interest

This section includes areas of interest whether due to observed safety findings, potential findings based on drug class, or safety topics anticipated to be requested by a regulatory agency for any reason. In general, potential adverse events of special interest (AESI) relevant to these special safety topics will be identified by one or more Standardized MedDRA Query(ies) (SMQs), by a Lilly-defined MedDRA PT listing based upon the review of the most current version of MedDRA, or by treatment-emergent relevant laboratory changes, as described below. Additional special safety topics may be added as warranted.

Unless otherwise specified, the special safety topics will be summarized for the Modified Safety Population and the All Lebrikizumab Modified Safety Population during their associated study periods as described in Section 6.1.4. Additional safety analysis may be added as needed.

Full details of the search terms and rules for deriving special safety topics in each of the sections below are described in the compound level safety standards along with information about the types of summaries and listings to be provided. In the event that the listing of terms or analysis changes for a special safety topic, it will be documented in the compound level safety standards which will supersede this document; it will not warrant an amendment to the individual study SAP.

6.14.6.1. Hepatic Safety

Hepatic labs include alanine aminotransferase (ALT), aspartate transaminase (AST), total bilirubin (TBL), and serum alkaline phosphatase (ALP).

Table KGAC.6.17. Summary Tables Related to Hepatic Safety

Analysis	Population
ALT and AST: The number and percentage of subjects with a measurement greater than or equal to 3 times (3X), 5 times (5X), and 10 times (10X) the performing lab upper limit of normal (ULN) during the treatment period for all subjects with a post-baseline value and for subsets based on various levels of baseline value	mS, mA
TBL and ALP: The number and percentage of subjects with a measurement greater than or equal to 2 times (2X) the performing lab ULN during the treatment period will be summarized for all subjects with a post-baseline value and for subsets based on various levels of baseline value	
Plot of maximum post-baseline ALT vs. maximum post-baseline total bilirubin	Modified Safety Population for All Periods: ever on lebri and never on lebri;

Abbreviations: ALP = serum alkaline phosphatase; ALT = alanine aminotransferase; AST = aspartate transaminase; lebri = lebrikizumab; mA = All Lebrikizumab Modified Safety Population; mS = Modified Safety Population; TBL = total bilirubin.

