3. STUDY DESIGN

This is a randomized, double-blind, placebo-controlled, parallel-group study which is 52 weeks in duration. The study is designed to confirm the safety and efficacy of lebrikizumab as monotherapy for moderate-to-severe atopic dermatitis utilizing a 16-week induction treatment period and a 36-week maintenance treatment period (Figure 1).

Eligible adult and adolescent (≥ 12 to < 18 years weighing ≥ 40 kg) patients with moderate-to-severe AD for at least one year, defined according to the American Academy of Dermatology Consensus Criteria, an EASI Score of ≥ 16 , an IGA score of ≥ 3 and a BSA of $\geq 10\%$ will be enrolled.

During the 16-week Induction Period, approximately 400 patients will be stratified and randomized 2:1 to either 250 mg lebrikizumab (loading dose of 500 mg given at Baseline and Week 2) or placebo by SC injection Q2W. All study drug injections will be administered in the clinic.

After completion of the Week 16 visit, patients who have responded to treatment [defined as having an IGA of 0 or 1 or a 75% reduction in EASI from Baseline to Week 16 (EASI-75)] will enter the Maintenance Period and will be re-randomized 2:2:1 to one of the following treatment groups: lebrikizumab 250 mg Q2W, lebrikizumab 250 mg Q4W, or placebo Q2W. Patients will be instructed to self-administer study drug at home.

Patients who do not achieve an IGA of 0 or 1 or an EASI-75 at Week 16 and those patients not maintaining an EASI-50 response following re-randomization at Week 24, 32, 40 or 48 will be assigned to an Escape Arm and receive lebrikizumab 250 mg as open-label treatment Q2W through Week 52. Patients not achieving an EASI-50 response after 8 weeks of treatment in the Escape Arm will be terminated from the study.

Efficacy will be measured through the IGA, EASI, BSA, SCORAD, Pruritus and Sleep-loss scores.

Safety will be assessed by monitoring adverse events, serum chemistry, hematology and urinalysis laboratory testing, physical examination, pulse and blood pressure. An independent Data Safety Monitoring Board will monitor patient safety by conducting formal reviews of accumulated safety data periodically throughout the trial. Additionally, adolescents will be monitored for hormones.

Quality of life and impact of disease will be assessed using the POEM, DLQI/CDLQI, EQ-5D and PROMIS Anxiety and Depression measures. Patients reporting comorbid asthma at study entry will complete the ACQ-5.

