5.1. Summary of Study Design

Study J2T-DM-KGAC (KGAC) [aka DRM06-AD05] is a randomized, double-blind, placebo-controlled, parallel-group study in adult and adolescent (≥ 12 to < 18 years weighing ≥ 40 kg) patients with moderate-to-severe atopic dermatitis (AD). Approximately 400 patients will be enrolled into the study. The study is comprised of 2 treatment periods (16-week Induction and 36-week Maintenance). Patients completing this 52-week study will be offered continued treatment in a separate long-term extension study J2T-DM-KGAA (DRM06-AD07). Patients who early terminate or choose not to enter the long-term extension study will undergo a follow-up visit approximately 12 weeks after the last study drug injection for safety follow-up.

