5.1.2. Baseline and Double-Blinded Induction Period (Week 0 to Week 16)

At baseline visit (Day 1), patients who meet the study eligibility criteria will be 2:1 randomly assigned to their induction treatments with stratification based on geographic region (United States [US] versus European Union [EU] versus rest of world), age (adolescent patients 12 to < 18 versus adults ≥ 18 years) and disease severity (IGA 3 versus 4). The treatment groups in the Blinded Induction Period are:

- Lebrikizumab 250 mg every 2 weeks (Q2W): 500 mg lebrikizumab administered at Baseline and Week 2 (loading dose; 2 pre-filled syringes with a pre-assembled needle safety device [PFS-NSD]) and 250 mg Q2W through Week 14.
- Placebo: 4 mL (2 PFS-NSD) administered at Baseline and Week 2 and 2 mL Q2W through Week 14.

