5.2. Determination of Sample Size

For FDA: In the DRM06-AD01 Phase 2b study (J2T-DM-KGAF), the proportion of patients who achieved an IGA score of 0 or 1 at Week 16 using the rescue medication non-response sensitivity analysis was approximately 34.7% for lebrikizumab 250 mg Q2W versus 7.7% for placebo. A sample size of 96 for lebrikizumab 250 mg Q2W versus 48 for placebo will have more than 95% power to detect a statistically significant difference based on a two group continuity corrected chi-square test with a two-sided significance level of 0.05. However, to ensure sufficient safety information is collected and to ensure sufficient responders for the Maintenance Period, the sample size will be increased to approximately 400 in total with a randomization ratio of 2:1 lebrikizumab:placebo.

For European Medicines Agency (EMA): In the DRM06-AD01 Phase 2b study (J2T-DM-KGAF), the proportion of patients who achieved an IGA score of 0 or 1 at Week 16 using the rescue medication non-response sensitivity analysis was approximately 34.7% for lebrikizumab 250 mg Q2W versus 7.7% for placebo, and the proportion of patients who achieved an EASI-75 at Week 16 using the rescue medication non-response sensitivity analysis was approximately

48.0% for lebrikizumab 250 mg Q2W versus 11.5% for placebo. A sample size of 96 for lebrikizumab 250 mg Q2W versus 48 for placebo will have more than 95% power to detect a statistically significant difference based on a two-group continuity corrected chi-square test with a two-sided significance level of 0.05 for each of the co-primary endpoints, which imply an overall power of at least 90%. However, to ensure sufficient safety information is collected and to ensure sufficient responders for the Maintenance Period, the sample size will be increased to 400 in total with a randomization ratio of 2:1 lebrikizumab:placebo.

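### The one ALT-by-bilirubin plot in the SAP compares ever with never on lebrikizumab over all periods, which leaves a small, non-randomised control; an Induction plot by randomised arm should be added

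*SAP*

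**What the plan says.** SAP Section 6.14.6.1 (Table KGAC.6.17) lists three hepatic displays. Two are threshold counts for single analytes: ALT and AST at 3, 5 and 10 times the upper limit of normal, and total bilirubin and alkaline phosphatase at 2 times. The third is the joint display: "Plot of maximum post-baseline ALT vs. maximum post-baseline total bilirubin". Its population entry reads "Modified Safety Population for All Periods: ever on lebri and never on lebri". The laboratory displays in SAP Section 6.14.3 work analyte by analyte.

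For patient flow, SAP Section 5.1 says "Approximately 400 patients will be enrolled into the study", and Section 5.1.2 says that patients "will be 2:1 randomly assigned to their induction treatments". Under Protocol Section 3, patients without a Week 16 response, and re-randomised patients who later lose EASI-50, "will be assigned to an Escape Arm and receive lebrikizumab 250 mg as open-label treatment Q2W through Week 52". SAP Section 5.1.3.2 sends patients rescued during Induction the same way. Week 16 responders (IGA 0/1 or EASI-75), including those from the placebo arm, are re-randomised 2:2:1 to lebrikizumab Q2W, lebrikizumab Q4W or placebo.

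**The concern.** A plot of peak ALT against peak bilirubin is where one looks for patients in whom both rise, and a control group shows how often that happens without the drug. Here the control is whoever never received lebrikizumab. The design moves most placebo patients onto the drug at Week 16, so that group is small and is selected by early departure or by response on placebo.

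Two further problems follow. First, follow-up is unequal. Post-baseline chemistry is scheduled at Weeks 8, 16, 32 and 52, or at early termination. A patient who leaves before Week 16 has about one or two draws, against up to four for one who continues, and a maximum over more draws tends to be larger. Second, the table does not say when post-baseline begins for a patient who switches from placebo. If it begins at the first study injection, a rise on placebo at Week 8 or 16 would be plotted in the lebrikizumab group.

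**Working it through.** **The plan's own figure.** The SAP gives no sizes for the ever and never groups. The planning rates used below come from its sample-size section (5.2), so that calculation was checked first. Inputs: IGA 0/1 "34.7% for lebrikizumab 250 mg Q2W versus 7.7% for placebo"; EASI-75 "48.0% for lebrikizumab 250 mg Q2W versus 11.5% for placebo"; 96 versus 48 patients; "two group continuity corrected chi-square test with a two-sided significance level of 0.05".

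Power = Φ[(Δ − c − 1.96·SE₀)/SE₁], with c = ½(1/96 + 1/48) = 0.0156.

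- IGA 0/1: pooled rate 0.257, SE₀ = 0.0773, SE₁ = 0.0620. (0.270 − 0.0156 − 0.1514)/0.0620 = 1.66, so power is 95.2%.
- EASI-75: pooled rate 0.358, SE₀ = 0.0848, SE₁ = 0.0687. (0.365 − 0.0156 − 0.1661)/0.0687 = 2.67, so power is 99.6%.

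Both agree with the stated figure of more than 95%.

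**Size of the never group.**

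- Randomised to placebo: 400 × 1/3 = 133.3.
- Placebo responders, r: response is IGA 0/1 or EASI-75, so r lies between 11.5% (every IGA responder also has EASI-75) and 7.7% + 11.5% = 19.2% (no overlap). That is 15 to 26 patients.
- Re-randomised to placebo: one fifth of these, 3 to 5 patients.
- Placebo patients leaving before Week 16, d: not stated, so taken as 0% to 20%.
- Later escape among those kept on placebo, e: not stated. The low end of each range uses e = 0.5 with r = 11.5%; the high end uses e = 0 with r = 19.2%.

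Never = 133.3 × [d + (r/5)(1 − e)]; ever = 400 − never.

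| d (assumed) | Never, low | Never, high | Share of placebo arm moved | Ever : never |
|---|---|---|---|---|
| 0% | 1.5 | 5.1 | 96–99% | above 75:1 |
| 5% | 8.2 | 11.8 | 91–94% | 33–48:1 |
| 10% | 14.9 | 18.5 | 86–89% | 21–26:1 |
| 15% | 21.5 | 25.1 | 81–84% | 15–18:1 |
| 20% | 28.2 | 31.8 | 76–79% | 12–13:1 |

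The randomised ratio is 2:1. At d = 5% the early leavers number 6.7, which is 57% to 81% of the never group, and their share rises with d. At most about 3 to 5 patients could serve as a placebo control through Week 52.

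The result is not sensitive to the placebo response rate. With r = 30% and d = 10%, the never group is 17 to 21.

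**What the smaller control costs.** If no control patient has a joint elevation, the one-sided 95% upper bound on the control rate is 1 − 0.05^(1/n): 2.2% for n = 133, 9.5% for n = 30, 17% for n = 16 and 63% for n = 3.

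**The case against.** The strongest reply is that the randomised comparison for liver safety is not lost. The ALT and AST thresholds are planned for the Modified Safety Population, where Table KGAC.6.2 sets lebrikizumab against placebo in Induction. Box plots, shift tables and treatment-emergent abnormal values are planned there too, and abnormal results are listed for all enrolled patients. The plot carries no test and still shows every patient with a joint elevation. All of this stands. A reader might infer that hepatic safety has no placebo control; the documents do not support that.

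A reader might also infer that placebo-period elevations will be counted against lebrikizumab. That is not established. SAP Section 6.1.2 ends the safety baseline period at the first Induction injection, which points that way. But Section 6.1.4 uses the Maintenance baseline for adverse events in patients first exposed then, Section 6.14.1 counts lebrikizumab exposure from the first lebrikizumab injection, and further definitions are left to the compound level safety standards. None of these rules is stated for the plot.

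Those standards are not part of the protocol or SAP, and under Section 6.14.6 documented changes to special safety topics there supersede the SAP. They may contain another joint display, so the claim that this is the only one holds for the two documents alone.

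Last, not every placebo non-responder must switch. Protocol Section 5.3.3 requires visit compliance for escape, and washout after systemic rescue. Patients who do not enter add to the never group, just as a higher d would.

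None of these points gives the joint plot a randomised control.

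**Conclusion.** The point holds as a cheap improvement. As written, the joint ALT–bilirubin plot sets about 368–398 patients ever on lebrikizumab against about 2–32 never on it, in place of the roughly 267 versus 133 available in Induction. This assumes 400 patients, the Phase 2b planning rates, up to half of the re-randomised placebo patients escaping, and placebo drop-out of 0–20%. Removal of Site 5042 is not quantified and would lower the counts.

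It would go too far to say that almost the whole placebo arm always moves: that fits drop-out up to about 10% (86–99% moved), but at 20% it is about three quarters. Counting placebo-period maxima as lebrikizumab values is a risk that depends on an unstated definition. The firm conclusion is narrower: this one display lacks the randomised comparison that the single-analyte displays keep.

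**What to change.** Add to Table KGAC.6.17 the same ALT–bilirubin plot for the Modified Safety Population in the Induction Period, by randomised arm (LEB250Q2W versus PBO). Keep the all-period ever/never plot as a labelled supplement, and state when post-baseline starts: for a patient who switches from placebo, values count in the ever group only after the first lebrikizumab injection. Replacing the all-period plot would be worse, because it would drop the post-Week 16 values of patients who stay on placebo.

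The cost is one more figure to produce and read, plus a line of SAP text. No new data are needed: chemistry is already scheduled at Weeks 8 and 16, and Table KGAC.6.2 already defines the comparison. SAP Section 3 records that the study team was unblinded to induction treatment before Version 5, so the added plot reveals no further assignment.

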6.14.6.2. Eosinophilia and Eosinophil-Related Disorders

In addition to the standard laboratory analysis (Section 6.14.3), eosinophilia and eosinophil-related AE will be summarized. Details regarding eosinophil-related PTs are in Compound Level Safety Standard.

Table KGAC.6.18. Summary Tables Related to Eosinophilia and Eosinophil-Related AE

Analysis	Population
Shift table summarizing the number and percentage of participants within each maximum baseline category versus each maximum postbaseline category by treatment	mS, mA
Summary of eosinophilia and eosinophil-related TEAE by PT	mS, mA

Abbreviations: AE = adverse event; PT = Preferred Term; mA = All Lebrikizumab Modified Safety Population; mS = Modified Safety Population; TEAE = treatment-emergent adverse event.

6.14.6.3. Infections, Including Herpes Infections and Relevant Parasitic Infections

Infections will be defined using the PTs from the MedDRA Infections and Infestations SOC. The MedDRA terms used to identify infections considered to be opportunistic infections (OI) in patients with immune mediated inflammatory conditions treated with immunomodulatory drugs are based on Winthrop et al. (2015) and are listed in the compound level safety standards. The list contains narrow (more specific) and broad (less specific) PTs with respect to these prospectively defined OIs. Definitions of herpes infections, parasitic infections and skin infections are listed in the compound level safety standards.

Table KGAC.6.19. Summary Tables/Listing Related to Infection Related AE

Analysis	Population
Summary of treatment-emergent infections by PT by maximum severity	mS, mA
Summary of serious infections by PT	mS, mA
Summary of infection AEs resulting in permanent study drug discontinuation	mS, mA
Treatment-emergent potential OI by PT nested with categories for narrow terms and broad terms separately	mS, mA
Treatment-emergent adverse events, herpes and parasitic infections	mS, mA
Treatment-emergent adverse events, skin infection	mS, mA
Summary and/or listing of Infection follow-up form	mS (summary only)
A listing of patients with potential OI, Serious Infection, herpes and parasitic infections	S

Abbreviations: AE = adverse event; OI = opportunistic infections; mA = All Lebrikizumab Modified Safety Population; mS = Modified Safety Population; PT = Preferred Term.

